2.1.3 Analysis methods for primary endpoint

Primary efficacy analysis:

• Intention-to-treat analyses will include the assigned treatment arms and results from all clusters. Incidence rates will be determined using a Poisson regression that models

counts of malaria episodes and includes an offset that accounts for log person-weeks. This yields a malaria rate per week per child per rainy season for intervention and control villages (averaged across year 1 and 2).

- The estimate for the primary analysis is the exponentiated beta coefficient for the treatment covariate across both seasons. This rate ratio corresponds to the difference in rates between treatment and control villages.
- Statistical Model:
 - The model below shows the outcome (malaria episodes), a coefficient for treatment group (intervention vs control), a coefficient for year (rainy season 1 vs rainy season 2), a coefficient for sex, an offset term to account for person-weeks, and a random effect to account for clustering at the village level.

Let Y_{hijk} be the number of malaria episodes for subjects k within village j within treatment i within year h

```
\begin{split} \log(Y_{ijk}) &= \alpha + \beta_1 X_i + \beta_2 X_{ijk} + \beta_3 X_{hijk} + \log(t_{hk}) + u_{ij} \\ \text{where } X_i &= 0 \text{ (control) or } X_i &= 1 \text{ (Ivermectin)}, \ X_{ijk} &= 0 \text{ (female) or } X_{ijk} &= 1 \text{ (male) and} \\ X_{hijk} &= 1 \text{ (Year 1) or } X_{hijk} &= 2 \text{ (Year 2) and:} \\ & \alpha &= \text{ Intercept} \\ & \beta_1 &= \text{ Log of the rate ratio treatment vs control} \\ & \beta_2 &= \text{ Log of the rate ratio males vs females} \\ & \beta_3 &= \text{ Log of the rate ratio Year 1 vs Year 2} \\ & \log(t_{hk}) &= \text{ Denotes log person-weeks} \\ & u_{ij} &= \text{ Denotes the random village effect} \end{split}
```

- Detailed simulation studies were used to determine the appropriate analysis procedure for this trial (Jackson, et al. *Trials* 2021)
- Software:
 - SAS v9.4 (SAS Institute Inc., Cary, NC) will be used for the primary statistical analyses.
 - A Kenward Roger degrees of freedom correction will be applied to account for the limited number of clusters
 - Code Example:

```
proc glimmix data=WORK.DataExample;
class Village_code Treatment YEAR Sex;
Model Episodes = Treatment Year Sex/ s dist=Poisson ddfm=kr offset =
InPersonWeeks;
Random INT / subject= Village_code;
Run:
```

2.2 Secondary endpoints

- **2.2.1** Adverse events analysis: Safety is a secondary endpoint and will be assessed by relative risk (RR).
 - a. Groups
 - All participants_will be followed actively and passively for adverse events and the Risk Ratios (RR) of AEs in those in the intervention versus control clusters will be compared.
 - ii. Active Case Detection Cohort

- SMC-treated children only children age 3-59 months who receive SMC. RR of AEs in children who receive SMC and live in IVM-treated clusters versus those who receive SMC and live in placebo-treated clusters
- 2. **IVM/placebo-treated only** children ≥90cm and eligible for MDA/placebo. RR of AEs in those children receiving MDA versus those receiving placebo.
- iii. **Non-ACD participants** that were enrolled in the study were actively followed in the study on the days of study intervention through 24-hours post study intervention, and then passively for the rest of the MDA round.
- b. **Type** AEs will be further classified by seriousness, severity, relationship to the intervention, outcome, and organ system.
 - i. Classification (AE, SAE, etc)

Adverse Event: (ICH) E6 defines an AE as any untoward medical occurrence in a patient or clinical investigation subject administered a pharmaceutical product regardless of its causal relationship to the study treatment. FDA defines an AE as any untoward medical occurrence associated with the use of a drug in humans, whether or not considered drug related. An AE can therefore be any unfavorable and unintended sign (including an abnormal laboratory finding), symptom, or disease temporally associated with the use of a medicinal product.

Serious AE (SAE): An AE is considered "serious" if, in the view of either the site principal investigator or sponsor, it results in any of the following outcomes:

- 1. Death.
- 2. A life-threatening AE: An AE is considered "life-threatening" if, in the view of either the site principal investigator or sponsor, its occurrence places the patient or subject at immediate risk of death. It does not include an AE that, had it occurred in a more severe form, might have caused death.
- 3. Inpatient hospitalization or prolongation of existing hospitalization.
- 4. A persistent or significant incapacity or substantial disruption of the ability to conduct normal life functions, or
- 5. A congenital anomaly/birth defect.
- 6. Important medical events that may not result in death, be life-threatening, or require hospitalizations may be considered serious when, based upon appropriate medical judgment they may jeopardize the patient or subject and may require medical or surgical intervention to prevent one of the outcomes listed in this definition. Examples of such medical events include allergic reaction requiring intensive treatment in an emergency room or at home, blood dyscrasias or convulsions that do not result in inpatient hospitalization, or the development of drug dependency or drug abuse.

ii. Severity (grade)

- Grade 1 (mild)
- Grade 2 (moderate)
- Grade 3 (severe)
- Grade 4 (potentially life-threatening)
- Grade 5 (death)

iii. Outcome

- recovered/resolved without sequelae (grade for the event returned to <2)
- recovering/resolving (grade for event is decreasing and not greater than 2)
- not recovered/not resolving (adverse event still present but stable)
- recovered/resolved with sequelae (grade for the event returned to <2, however some pathological condition resulting from a disease, injury, or other trauma)
- Death
- unknown (example for using this code is when a participant is lost to follow up and outcome cannot be determined)
- iv. **By body system and preferred term** using MedDRA coding (27 groups)

2.2.2 Parasitological secondary endpoints and analysis.

The following are key secondary parasitological endpoints, and the method of analysis will depend on the type of data collected:

- Parasite prevalence. Parasite prevalence of *Plasmodium falciparum* will be assessed either by:
 - molecular assay (PCR-based off of filter paper from capillary finger-prick samples). Filter paper samples are obtained at the beginning and end of each intervention season, and monthly, prior to each MDA in the ACD cohort. In addition, filter paper was obtained in the entire cohort at the beginning and end of the 2020 intervention season.
 - blood smear (only for ACD children at the time of diagnosed malaria infection by RDT)
- Multiplicity of infection (MOI, also sometimes referred to as complexity of infection (COI). This is defined as the number of unique clones per individual at the time of diagnosis of malaria infection (count data). It is based either on microsatellite typing or amplicon sequencing
- Molecular force of infection (mFOI; also sometimes further subclassified as molFOB (molecular force of blood stage infection). Defined as the number of new *Plasmodium* clones acquired over time (count data). Will be determined using monthly filter paper samples in ACD children only.

An approach consistent with the primary analysis will be adopted here with both unadjusted and adjusted regression models. For parasite prevalence, a binomial regression model will be used, and for MOI and mFOI, Poisson and Negative Binomial regression model will be used, with the final model choice being indicated by the distribution of the dependent variable.

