### 3.2.2. Secondary

- AE monitoring will occur both actively and passively. All AE will be graded and analyzed by seriousness, intensity and causality. AE monitoring in this study is crucial to properly weigh the potential benefits vs. potential risks of the study.
- In the entire enrolled populace, passive monitoring of AEs will occur through spontaneous reporting of events to the study clinical team, and recorded on CRFs. AEs will be recorded from the entire enrolled populace, regardless if they were treated with ivermectin/placebo or not eligible to take the intervention. AEs will also be actively monitored on the days of distribution of ivermectin/placebo through direct questioning of AEs and recording on CRFs by study nurses for all participants. AE will be recorded over the intervention period occurring during the 1st and 2nd rainy seasons. More specifically, AEs will be recorded from the start of the first MDA of each rainy season to 1 month after the last MDA of that season.
- For those children enrolled in the active case detection cohort, where children are visited weekly to assess for malaria incidence, active monitoring of AEs will occur through direct questioning of AEs by the study team. Additionally, passive monitoring of AEs will occur by

---

participants spontaneously reporting directly to the nurses when the nurses are in the villages performing active case detection of malaria in the child cohort, or spontaneously reporting indirectly to the nurses via communication through the village community health worker (who will then communicate the AE directly to the nurse or field physician).

- For women that become pregnant during the intervention period, monitoring for birth outcomes will be conducted. Pregnancies will be followed in both arms of the study.
- Entomological indices will provide a first-order mechanistic explanation of the intervention's effect on malaria incidence (the primary outcome): Wild, blood-fed, indoor-aspirated, *Anopheles* will be held in cages and scored for survival rates over time, which will be analyzed across arms. The age structure of captured *Anopheles* will be analyzed over time and analyzed across arms. Captured wild mosquitoes will be dissected and analyzed for sporozoite infection rates over time and analyzed across arms. A cohort of participants' sera immuno-reactivity to an *Anopheles* saliva antigen will be analyzed over the intervention period of each season.

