## 8. ASSESSMENT OF SAFETY

### 8.1. Definitions

**Adverse Event (AE):** (ICH) E6 defines an AE as any untoward medical occurrence in a patient or clinical investigation subject administered a pharmaceutical product regardless of its causal relationship to the study treatment. FDA defines an AE as any untoward medical occurrence associated with the use of a drug in humans, whether or not considered drug related.

An AE can therefore be any unfavorable and unintended sign (including an abnormal laboratory finding), symptom, or disease temporally associated with the use of a medicinal (investigational) product. The occurrence of an AE may come to the attention of study personnel during study visits and interviews of a study recipient presenting for medical care, or upon review by a study monitor.

All AEs, will be captured on the appropriate data collection form. Information to be collected for AEs includes event description, date of onset, an assessment of severity, relationship to study product and alternate etiology (assessed only by those with the training and authority to make a diagnosis), date of resolution, seriousness, and outcome. AEs occurring during the trial collection and reporting period will be documented appropriately regardless of relationship. AEs will be followed through resolution.

Any medical condition that is present at the time that the subject is screened will be considered as baseline and not reported as an unsolicited AE. However, if the severity or frequency of any pre-existing medical condition increases, it will be recorded as an unsolicited AE.

If an event meets both the criteria of a study endpoint and an adverse event, the event will be reported either as a study endpoint or as an adverse event (not both).

**Serious Adverse Event (SAE):** An AE is considered “serious” if, in the view of either the site principal investigator or sponsor, it results in any of the following outcomes:

- Death,
- A **life-threatening AE:** An AE is considered “life-threatening” if, in the view of either the site principal investigator or sponsor, its occurrence places the patient or subject at immediate risk of death. It does not include an AE that, had it occurred in a more severe form, might have caused death.
- Inpatient hospitalization or prolongation of existing hospitalization,
- A persistent or significant incapacity or substantial disruption of the ability to conduct normal life functions, or

- A congenital anomaly/birth defect.

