Instead, the interim analyses of safety (AEs), relative to the expected benefits in possible reduced malaria incidence in the cohort and reduced NTD among the treated populace, will provide the main data points for consideration of early halting of the trial. The expected AE incidence of the present study can be estimated from the RIMDAMAL I and IVERMAL trials, and used to decide if drug-related AE incidence is abnormally high relative to the expected benefit. The RIMDAMAL I trial had a dosing regimen of 150-200 µg/kg every 3 weeks for 18 weeks (6 treatments) to eligible participants in villages of the same region as this study. This resulted in AE being observed in 3% of the entire population of the study arm (45 AE in 1447 participants). However only ~75% of these participants were repeatedly treated with drug in the arm, and only 5 of these AE were considered possibly or probably related to the intervention (5/787 treated participants; 0.6%). All were classified as standard AE (see Appendix B) of mild or moderate intensity that consisted of vomiting, pruritus, edema in the limbs, or tremors. In the IVERMAL trial, 48 adult participants with confirmed symptomatic uncomplicated *Plasmodium falciparum* malaria were treated with one dose of an ivermectin regimen consisting of 3 days of 300 µg/kg/day that was co-administered with a 3-day course of dihydroartemisinin-piperaquine. This resulted in 8% (4/48) participants having an AE, but only 4% (2/48) of which were considered treatment-related. These AE were minor visual disturbances. Neither trial observed any treatment-related SAE.

Each round of MDA is given to the entire study population over the course of 3 days. Data on AEs/SAEs will accumulate over the course of the month following each MDA, and data will be entered into the eCRFs. Thus, the data at the end of each round of MDA should capture all enrolled individuals by either active or passive follow-up. The study team will review these data on an ongoing basis for any concerning safety signals. It is anticipated that the first full safety review of the initial round of MDA will

---

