## 10. STATISTICAL CONSIDERATIONS

### 10.1. Study Hypotheses

The primary objective hypothesis is that repeated IVM MDAs (the intervention) coinciding with SMC rounds and other standard-of-care malaria control measures (LLIN distribution, IPTp) will significantly reduce the incidence of childhood malaria compared to the placebo intervention. This hypothesis will be tested in a 2-arm superiority trial with a cluster randomized design. The primary outcome measures of incidence of malaria episodes among village children ≤ 10 years of age in each arm will be used to test the hypothesis. The primary objective null hypothesis is that that repeated IVM MDAs coinciding with SMC rounds and other standard-of-care malaria control measures will have no effect on the incidence of childhood malaria compared to placebo MDAs coinciding with SMC rounds and other standard-of-care malaria control measures.

Secondary objective hypotheses:

- The risk of adverse events (AEs) per participant in the intervention arm occurring over the intervention phase of the trial will not differ relative to the risk of adverse events in the control arm.  
*Null: The risk of adverse events (AEs) per participant in the intervention arm occurring over the intervention phase of the trial will not differ relative to the risk of adverse events in the control arm.*
- The survival rates of wild blood fed *Anopheles gambiae* s.l. will be significantly reduced, and age-structure and entomological inoculation rate in wild *Anopheles gambiae* s.l. significantly younger/lower, in those captured from intervention arm villages as compared to those captured control arm villages at equivalent time intervals during the intervention phase. Also, the immuno-reactivity of intervention-arm participants' IgG over time to an *Anopheles* salivary gland peptide will be significantly lower than that from control arm participants.  
*Null: The survival rates of wild blood fed Anopheles gambiae s.l., and parity and sporozoite rates in wild Anopheles gambiae s.l., will not differ in those captured from intervention arm villages as compared to those captured control arm villages at equivalent time intervals during the intervention phase. Similarly, the immuno-reactivity of intervention-arm participants' IgG over time to an Anopheles salivary gland peptide will be no different than that from control arm participants.*

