3. PLANNED TABLES, FIGURES, LISTINGS

Manuscript Tables:

- 1. Participant characteristics
- 2. Primary efficacy analyses
- 3. Adverse events
- 4. Subgroup analysis of malaria risk

Manuscript Figures:

- 1. CONSORT diagram
- 2. Map of study area
- 3. Rainfall and weekly malaria incidence

Supplementary appendix tables:

- S2.1: Percentage reduction in clinical incidence during the trial period
- S3.1: Risk in epidemiological strata
- S3.2: Exploratory analysis of the frequency of malaria episodes per child in each group

Figures: Supplementary appendix

- S1.1: Map of study area
- S2.1: Estimated reduction in clinical incidence
- S3.1: Flow diagram for all RIMDAMAL participants with respect to MDA participation and AE analysis.
- S3.2: Weekly malaria incidence per person-year in the RIMDAMAL study cohort children plotted over the study period.

Supplementary appendix Listing:

- S4.1: Descriptions of reported adverse events (AE) in RIMDAMAL villages (excluding uncomplicated malaria recorded from the child cohort.
- S4.2: Summary of deaths during intervention season

Additional figures/tables:

- Seasonality: Risk by month with rainfall
- Interaction of Interceptor G2 bed net distribution by cluster/HH/individual (only in 2020)
- Interaction of proportion of people treated per cluster and over time.
- MOI
- mFOI
- anemia
- entomology outcome figures

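### The all-participant AE and SAE risk ratios appear to include malaria outside the child cohort, so they mix an expected malaria benefit with any drug harm, and no non-malaria ratio is planned beside them

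*SAP*

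**What the plan says.** SAP 2.1 plans risk ratios and attributable risks, with 95% confidence intervals, for AEs and SAEs by arm. SAP 2.2.1 repeats this for all participants: "the Risk Ratios (RR) of AEs in those in the intervention versus control clusters will be compared". Protocol 10.1 frames the safety hypothesis in the same all-cause terms: the AE risk per participant in the intervention arm "will not differ relative to the risk of adverse events in the control arm".

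What counts as an AE is broad. SAP 2.2.1 uses the standard definition, "any untoward medical occurrence in a patient or clinical investigation subject administered a pharmaceutical product regardless of its causal relationship to the study treatment". Protocol 3.2.2 adds that "AEs will be recorded from the entire enrolled populace, regardless if they were treated with ivermectin/placebo or not eligible to take the intervention".

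Two places bear on whether malaria is in the count:

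- Protocol 8.1 says that when something is both an endpoint and an AE, "the event will be reported either as a study endpoint or as an adverse event (not both"). It does not say which.
- The title of listing S4.1 in SAP 3 reads: "Descriptions of reported adverse events (AE) in RIMDAMAL villages (excluding uncomplicated malaria recorded from the child cohort").

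Protocol 7.4 groups complicated malaria with SAEs. Protocol 2.3.2 expects malaria to fall among people living in intervention villages.

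**The concern.** Malaria is a study endpoint only in children aged 10 or under. For anyone older, the either/or rule in protocol 8.1 gives no reason to take a malaria illness out of the AE count, and the S4.1 exclusion does not reach it. Complicated malaria in cohort children is also untouched by S4.1, so the SAE ratio is affected inside the cohort as well.

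If malaria is in the count and the intervention lowers it, the all-cause ratio combines a component below 1 (less malaria) with one that may be above 1 (drug-caused events). The first secondary objective is to learn whether ivermectin MDA increases harms. A ratio near 1 would fit the stated hypothesis of no difference, yet it could arise either from no drug harm or from a harm offset by fewer malaria illnesses. The planned all-participant comparison cannot tell these apart.

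**Working it through.** **Inputs from the documents**

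- Modelled malaria reduction, children aged 10 or under (protocol 10.2, SAP 1.3): 1 − 0.619/1.088 = 0.431. The stated 43.1% is reproduced.
- Malaria reduction in the pilot trial, children aged 5 or under (protocol 2.1): 1 − 2.00/2.49 = 0.197, stated as a risk ratio of 0.80. I use 20%.
- Pilot control-arm AE risk (protocol 2.1): 24/1265 = 1.9%.
- Pilot risk of AEs judged possibly or probably related (protocol 8.4): 5/787 = 0.64%.

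**Not in the documents, so assumed**

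- The malaria share *m* of control-arm AEs: 0.1 to 0.5.
- The ratio for all other AEs: 1.3.
- The malaria reduction *e* outside young children: the two child figures are borrowed.

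**Illustration 1: by share of AEs**

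All-AE ratio = m(1 − e) + (1 − m) × 1.3

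| m | e = 0 | e = 20% | e = 43.1% |
|---|---|---|---|
| 0.1 | 1.27 | 1.25 | 1.23 |
| 0.3 | 1.21 | 1.15 | 1.08 |
| 0.4 | 1.18 | 1.10 | 1.01 |
| 0.5 | 1.15 | 1.05 | 0.93 |

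For example, at m = 0.3 and e = 43.1%: 0.3 × 0.569 + 0.7 × 1.3 = 0.171 + 0.910 = 1.08. The e = 0 column shows that part of the fall is plain dilution by events unrelated to the drug. The malaria benefit adds the rest.

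The ratio reaches 1 at m = 0.3/(0.3 + e). That is 0.41 for e = 43.1%, and 0.60 for e = 20%, which lies outside the assumed range.

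**Illustration 2: by absolute risk**

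Let b be the non-malaria AE risk (1.9%, borrowed from the pilot's all-AE control risk), h the drug-caused risk (0.6%), and now let m be the malaria AE risk itself.

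- Control risk = 1 − (1 − b)(1 − m)
- Ivermectin risk = 1 − (1 − b)(1 − h)(1 − m(1 − e))

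| m | e = 0 | e = 20% | e = 43.1% |
|---|---|---|---|
| 0 (malaria excluded) | 1.31 | 1.31 | 1.31 |
| 1% | 1.20 | 1.13 | 1.06 |
| 5% | 1.08 | 0.94 | 0.77 |

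For example, at m = 1% and e = 43.1%: control risk 2.881%, ivermectin risk 3.043%, ratio 1.06. With malaria excluded, the ratio depends on neither unknown.

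**A rough bound from the pilot**

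Had every control-arm AE there been malaria, the offset would be at most 1.9% × 0.20 = 0.38 percentage points, or 1.9% × 0.431 = 0.82 points. Against a related-AE risk of 0.64%, complete offset is possible only towards the larger reduction.

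**Would malaria outside the cohort be recorded?**

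Partly. SAP 2.2.1 has active follow-up there only to 24 hours after dosing, then passive reporting. The protocol summary adds weekly AE visits to transect households. Protocol 7.7 provides unscheduled nurse visits open to all participants and foresees that some will meet the malaria definition.

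**The case against.** **All-cause is the stated question.** Protocol 10.1 asks about AE risk per participant. For net harm in the village, the all-cause ratio by arm is the right contrast and is not biased. This stands. It is a reason to keep that ratio, not a reason to omit a second one.

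**The plan offers other views of harm.** A reader might infer that safety comes down to one number. It does not. SAP 2.2.1 also plans ratios within the cohort, for SMC-treated children and for children given ivermectin or placebo, where uncomplicated malaria is apparently out. AEs are also classified by relationship and MedDRA preferred term. This partly mitigates the concern. But relatedness is a clinical judgement, and no between-arm ratio is specified for related or non-malaria events. The cohort ratios also miss many dosed people. About 0.75 × 2,500 = 1,875 per arm are to be dosed. Even if all of roughly 900 cohort children per arm (half of about 1,800) were dosed, some 975 would lie outside the cohort.

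**The halting guideline is not affected in the same way.** Because protocol 8.4 weighs AEs "relative to the expected benefits in possible reduced malaria incidence in the cohort", a reader might infer that the malaria benefit enters both sides of the DSMB's comparison. The documents do not support that. The thresholds in 8.4 concern treatment-related events, and the benefit named is in the cohort, whose uncomplicated malaria is apparently not an AE. Protocol 10.3.1 does send the DSMB between-arm AE risk ratios, so a non-malaria ratio would still be useful there.

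**Counting malaria outside the cohort is an inference.** No sentence states it, and capture is mostly passive. S4.1 is a listing title, not a rule for the ratio. This stands, and it is why the point says malaria appears to stay in.

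**The pilot argues against strong masking.** Its AE ratio was 1.63 despite about 20% less child malaria. It would be tempting to treat 1.63 as a non-malaria ratio and work down from it. That would be wrong, because it is already an all-AE ratio from an arm with reduced malaria.

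**Conclusion.** The point holds as a gap in the safety analysis, not as proof that harm will be hidden. The all-participant AE and SAE ratios are all-cause, the only stated malaria exclusion is narrow, and the expected malaria reduction pulls these ratios down. A ratio near 1 would therefore not be enough to conclude that the drug does no harm.

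The size cannot be fixed from the documents. If other AEs had a ratio of 1.3, the all-AE ratio would be 1.23 to 0.93 with a 43.1% reduction and 1.25 to 1.05 with a 20% reduction, over malaria shares of 0.1 to 0.5. Complete masking within that range needs the larger reduction and a share of at least 0.41. The share, the 1.3 and the use of child reductions for older people are all assumptions, and part of each shift is dilution. This is a cheap improvement to the SAP rather than a flaw that undermines the trial.

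**What to change.** In SAP 2.1 and 2.2.1:

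- Keep the all-cause AE and SAE ratios as planned. Pre-specify beside them between-arm ratios for AEs and for SAEs excluding malaria-coded MedDRA terms, in all participants, with the term list and coding settled blind to arm.
- State how malaria is classified inside and outside the cohort, including complicated malaria in cohort children, where protocol 8.1 leaves the choice between endpoint and AE open.
- Report malaria outside the cohort separately, as a malaria outcome.
- Keep complicated malaria and malaria deaths in the all-cause SAE listing.
- Give the DSMB both ratios.

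The cost is SAP wording and extra lines in the AE tables, since MedDRA coding is already planned. One limit remains: febrile events without an RDT cannot be assigned to malaria and will stay in the non-malaria count, so some malaria effect will remain there.
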